Objectives of the Clinical Investigation Plan

The purpose of this study is to evaluate the sensitivity and specificity of the Belun Ring Pulse Oximetry system for screening of obstructive sleep apnea (OSA) in adults during standard polysomnography sleep study conditions. The primary outcome metric is the Apnea-Hypopnea Index (AHI).

The goal, in its entirety, is to evaluate the performance of the Belun Ring Pulse Oximeter during a standard polysomnography sleep study and its ability to compare to the determined Apnea-Hypopnea Index (AHI) of the subjects.

Identification and Description of the Investigational Device

Investigational Device: Belun Ring Oximeter

All appropriate testing will be performed and will demonstrate safety and efficacy for use in human studies prior to at . Such documentation will reside in the design history documentation. Testing of these devices will include: patient leakage, dielectric strength,

surface temperatures and biocompatibility testing. The sensors are the components expected to come in contact with the subjects.

The staff is familiar with the use of pulse oximetry monitors and the application of sensors. Additional training will be provided by the sponsor.

Risks and Benefits of the Investigational Device and Clinical Investigation:

Currently the FDA defines pulse oximeters as Class II devices which transmit radiation at a known wavelength(s) through blood and to measure the blood oxygen saturation based on the amount of reflected or scattered radiation and may be used alone or in conjunction with a fiberoptic oximeter catheter. All oximeters being used in this study work by transmittance of radiation at known wavelength(s) through tissue to measure blood oxygen saturation based on the amount of reflected and scattered radiation. **The devices under test in this study are thereby considered non-significant risk devices.**

For the purpose of this study:

- It is not intended as an implant.
 - Pulse oximetry sensors are applied to the surface of the site (such as forehead, ears and fingers) and is removed following data collection typically less than 1 day.
 - Sensors may be warm to the touch but are not expected to overheat during normal operations
 - Clip on sensors, the forehead headband may exert a small amount of pressure with mild discomfort
 - Adhesives may cause some skin irritations.

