The benefits to the study are to the advancement of non-invasive medical monitoring of patients by improving accuracy and performance of pulse oximeters. There are no direct benefits to the subjects participating in this study other than being a paid volunteer. The only alternative to this study is to NOT participate.

Design of the Clinical Investigation

Method

This study is a comparative, non-randomized study in a minimum of 50 subjects. Each subject test is expected to take up to 10 hours. The overall data collection process is expected to be completed in 2 - 4 months.

Subjects will be provided an IRB approved Informed Consent. As applicable, subjects will be told about any new information that might change their decision to participate. Subjects who have completed the informed consent and meet inclusion criteria and none of the exclusion criteria will be enrolled in the study.

Subjects will sleep for the duration of the study.

To avoid bias in the data collection, the ring size that best fits the subject will be selected.

Endpoint / Comparator

The primary objective of this study is to evaluate the ability of the Belun ring pulse oximeter to correctly gauge the Apnea-Hypopnea Index (AHI). Traditional PSG data will be used as the basis for comparison for the Belun ring pulse oximeter. The study population will include a minimum of fifty (50) subjects. All data will be used for the analysis unless identified as unstable. Data that is found to be unstable will be removed prior to the comparative analysis. For the statistical analysis, A Pearson's correlation will be used to determine the accuracy performance of the sleep score generated by the Belun Ring Oximeter to the AHI score generated from the PSG data. The sensitivity and specificity values of the Belun sleep scores will be computed respectively in the three levels of sleep apnea severity (mild AHI ≥ 5 , moderate AHI ≥ 15 , and severe ≥ 30). The area under the receiver operating characteristic (ROC) curve will also be calculated.

There are no deviations expected from this investigation plan, Should deviations be needed, discussions will be conducted with the Sponsoring company, Principal investigator and reported to the IRB as appropriate.

Study Population

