3. Explain the procedure to the subject. Have them read the Informed Consent Form, and review the information answering all questions. Once all questions have been answered, have the subject sign the form. Each subject will be given a copy of the consent form prior to release.

4. Based on the responses record accepted or declined from the study. Continue if accepted into the study.
5. Record subject information. Subject number and demographics information for subject description.
6. Apply all polysomnography equipment as is appropriate for the prescribed polysomnography study.
7. Measure both index fingers to find the correct ring size.
8. Apply the correct size Belun Ring Oximeter (device under test).
9. Conduct the polysomnography study as prescribed by the patient's physician while recording information from the Belun Ring Oximeter (device under test).
10. The clinician will review any final questions with the subject and ask if there were any effects from the study. The subject will be provided with phone numbers for questions pertaining to participation in this study or research-related injury or reaction post the study. The subject will be informed of the follow up procedure post the study.

The test sensor(s) will be placed on fingers, rotating sites where appropriate.

Monitoring Arrangements

Monitoring Plan:**Statistical Analysis**

A Pearson's correlation between sleep score generated by the Belun software and AHI generated by the PSG analysis will be calculated. The Belun sleep score will be tested separately against three AHI cut-off points representing three levels of sleep apnea severity (mild AHI ≥ 5 , moderate AHI ≥ 15 , and severe ≥ 30). The sensitivity and specificity values of the sleep scores will be computed respectively against the three AHI thresholds listed above. The area under the receiver operating characteristic (ROC) curve will also be calculated. Data analysis & demographics will be presented in final report

Deviations from the Statistical Plan

Any deviations from this statistical plan will be described and justified in the final report.

Data and Quality Management / Confidentiality

Study Documentation / Case Report Forms

Study procedure

"Validation of a novel device for screening patients with symptoms of obstructive sleep apnea"
Study ID# PR 2018-259

Amendments to the Clinical Investigation Plan

Deviations from the Clinical Investigation Plan

Device Accountability

Packaging and Labeling

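### Pearson's correlation, named as the measure of the ring's accuracy, cannot detect systematic bias against PSG AHI, and sensitivity and specificity would do so only with score cut-offs that the plan does not fix

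*Combined protocol and SAP*

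**What the plan says.** Under Design of the Clinical Investigation, the Endpoint / Comparator section states the aim: "The primary objective of this study is to evaluate the ability of the Belun ring pulse oximeter to correctly gauge the Apnea-Hypopnea Index (AHI"). The reference is PSG: "Traditional PSG data will be used as the basis for comparison for the Belun ring pulse oximeter". The same paragraph assigns the accuracy question to a correlation: "A Pearson's correlation will be used to determine the accuracy performance of the sleep score generated by the Belun Ring Oximeter". The Statistical Analysis section opens with it again: "A Pearson's correlation between sleep score generated by the Belun software and AHI generated by the PSG analysis will be calculated".

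Two further analyses are planned. One is the ROC area. The other is classification performance: "The sensitivity and specificity values of the sleep scores will be computed respectively against the three AHI thresholds listed above", the thresholds being "mild AHI ≥ 5 , moderate AHI ≥ 15 , and severe ≥ 30". This second analysis matches the Objectives section, which says "The purpose of this study is to evaluate the sensitivity and specificity of the Belun Ring Pulse Oximetry system".

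The text provided contains no mean difference, limits of agreement, concordance or intraclass coefficient, calibration slope, or acceptance criterion. It gives thresholds on PSG AHI but no cut-off on the Belun score, and it does not state the units of that score.

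**The concern.** Whether a device gauges AHI correctly is a question of agreement: how far is its reading from the PSG value, and in which direction? Pearson's r answers a different question, namely how closely the paired values follow some straight line with positive slope. The line need not be the line of identity. A ring that systematically over-reads or under-reads AHI can therefore produce a correlation near 1, and that correlation would be reported as its accuracy.

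r also depends on how widely AHI varies in the sample. The same device with the same error gives a higher r in a sample spread across all severity bands than in a mostly mild one, so r does not carry over from one population to another.

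**Working it through.** The plan gives no target correlation, agreement margin or sample-size derivation, so there is no figure of its own to reproduce. The AHI thresholds (5, 15, 30), the minimum of 50 subjects and the rough spread over four bands come from the documents. The AHI distribution within bands, the severe-band ceiling, the error SDs and the bias factors are assumptions.

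**1. Invariance (no assumptions about the data).** Let X be PSG AHI and S = a + b(X + e), with b > 0 and e independent of X. Then r = SD(X) / √(Var(X) + Var(e)). Neither a nor b appears, and without error r = 1. The ROC area depends only on the rank order of S, so it too is free of a and b.

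**2. Simulation.** 1,000 replicates of n = 50; AHI uniform within 0–5, 5–15, 15–30 and 30–80, split 13/13/12/12; error SD 3 events/h; score cut at 5/15/30. Triplets are for AHI 5 / 15 / 30.

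| Ring reads | r | AUC | Mean bias | 95% limits of agreement | Sensitivity | Specificity |
|---|---|---|---|---|---|---|
| AHI | 0.990 | 0.973 / 0.993 / 0.998 | 0.0 | −5.8 to 5.9 | 0.96 / 0.96 / 0.98 | 0.78 / 0.94 / 0.98 |
| AHI + 10 | 0.990 | 0.972 / 0.993 / 0.998 | +10.0 | 4.2 to 15.9 | 1.00 / 1.00 / 1.00 | 0.01 / 0.44 / 0.79 |
| half AHI | 0.990 | 0.972 / 0.992 / 0.998 | −10.9 | −32.1 to 10.3 | 0.82 / 0.53 / 0.40 | 0.99 / 1.00 / 1.00 |
| double AHI | 0.990 | 0.972 / 0.992 / 0.998 | +21.9 | −21.7 to 65.5 | 0.99 / 1.00 / 1.00 | 0.50 / 0.60 / 0.67 |

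With error SD 5, r is 0.974 in all four rows. The last-digit AUC differences are simulation noise.

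**3. Milder proportional bias, by hand.** Equal bands, no random error, score = k × AHI. The band means are 2.5, 10, 22.5 and 55, so the overall mean is 22.5. For k = 0.75:

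- Mean bias: −0.25 × 22.5 = −5.6 events/h.
- A score of 30 needs AHI 40, so sensitivity at AHI ≥ 30 is (80 − 40)/50 = 80%.
- Wrong class: AHI 5–6.67 (16.7% of its band), 15–20 (33.3%) and 30–40 (20%). Over four bands this is (0 + 16.7 + 33.3 + 20)/4 = 17.5%.

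The same steps give 93% sensitivity and 6% misclassified at k = 0.90, and 60% and 35% at k = 0.60. In every case r = 1.00. The severe-band ceiling matters: at k = 0.75, sensitivity is (60 − 40)/30 = 67% with a ceiling of 60, and (100 − 40)/70 = 86% with a ceiling of 100.

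**4. Cut-offs chosen from the data.** For the same 0.75 × AHI ring, score cut-offs of 3.75, 11.25 and 22.5 (0.75 × 5, 15, 30) give sensitivity and specificity of 100% at all three thresholds. The bias is absorbed and nothing in the planned output would show it.

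**5. Effect of spread.** Unbiased ring, error SD 8 (variance 64).

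- Equal bands: mean within-band variance (2.08 + 8.33 + 18.75 + 208.33)/4 = 59.4; between-band variance (20² + 12.5² + 0² + 32.5²)/4 = 403.1; total 462.5. r = √(462.5/526.5) = 0.94.
- Assumed milder mix of 60/25/10/5%: mean 9.0, E(X²) = 246.25, variance 246.25 − 81 = 165.25. r = √(165.25/229.25) = 0.85.

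**The case against.** The strongest reply is that Pearson is not the whole plan. Sensitivity and specificity at three AHI thresholds are also planned, they match the stated screening purpose, and they bear directly on misclassification. If the score is cut at 5/15/30, the 80% and 60% sensitivities in step 3 would appear in the report. A reader might infer that nothing in the plan could detect bias, or that r is its designated primary statistic. The documents support neither: the threshold analyses can react to bias, and no single statistic is called primary. What remains is that their ability to react depends on score cut-offs that the plan leaves open.

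Second, the output is called a sleep score. If it is a surrogate index rather than events/h, a mean difference from AHI is undefined, and association plus ROC is a reasonable screening analysis. That is fair, and it makes the score's scale the first thing to settle. It does not rescue r as a measure of how correctly AHI is gauged.

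Third, a reader might infer that the ring must under-read because it counts events per recorded hour while PSG, which includes EEG, counts per hour of sleep. The documents give no denominator for either index, so this is conjecture. Nor do they fix the AHI spread: the band sizes are approximate expectations, they total 40 of at least 50 subjects, and the top band is open-ended.

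**Conclusion.** The point holds in a limited form. The statistic that the plan assigns to accuracy cannot answer its primary objective, and the ROC area shares the defect. The threshold analyses could expose a shift or rescaling, but as written they are not guaranteed to. The invariance of r and AUC is algebra and rests on no assumption. The sizes do rest on assumptions: for bias factors of 0.90, 0.75 and 0.60, r stays at 1.00 (no random error) while about 6%, 17% and 35% of subjects are misclassified, given equal bands, a severe band of 30 to 80, and a score read on the AHI scale. These factors illustrate the problem; they are not estimates for this device. The spread effect, 0.94 against 0.85, likewise depends on the assumed mix and error SD.

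**What to change.** Amend Endpoint / Comparator and Statistical Analysis together:

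1. State the scale of the sleep score. Fix its conversion to events/h, and its cut-offs for the 5/15/30 analyses, before the ring and PSG data are merged.
2. Make the accuracy analysis the mean difference (ring minus PSG AHI) with its 95% CI, and Bland-Altman 95% limits of agreement with CIs. Use regression-based or ratio limits if the differences change with AHI.
3. Keep Pearson's r as descriptive, and keep the planned sensitivity, specificity and AUC.

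A concordance coefficient and a 4 × 4 severity table are optional.

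The paired data already planned are enough. At n = 50 the 95% CI half-width is t₀.₉₇₅,₄₉/√50 = 0.28 SD of the differences for the mean bias, and t₀.₉₇₅,₄₉ × √(1/50 + 1.96²/98) = 0.49 SD for each limit. The cost is plan wording and a little more analysis. The drawback for the sponsor is that the reported agreement may look less favourable than r.

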Official Title:

Validation of a novel device for screening patients with symptoms of obstructive sleep apnea

Study ID# PR 2018-259

NCT number: NCT04121923

COMMERCIAL SPONSOR:

Belun Technology Company Ltd.

**Document
Ownership:**

**Document
Approver:**

**Revision
History:**

Revision	Date	Revision Description
Version 1	02/01/18	Original issue
Version 2	02/27/18	Incorporated

Author:

**Validation of a novel device for screening patients with symptoms of obstructive sleep
apnea
Study ID# PR 2018-259**

ETHICS COMMITTEE REVIEW:

STUDY PROCEDURE:

Validation of a novel device for screening patients with symptoms of obstructive sleep apnea
Study ID# PR 2018-259

COMMERCIAL SPONSOR:

PRINCIPAL INVESTIGATOR:

SUB-INVESTIGATORS

MEDICAL OVERSIGHT:

STUDY SITE:

CONFIDENTIALITY:

Validation of a novel device for screening patients with symptoms of obstructive sleep apnea

Study ID# PR 2018-259

Synopsis

Objectives of the Clinical Investigation Plan

The purpose of this study is to evaluate the sensitivity and specificity of the Belun Ring Pulse Oximetry system for screening of obstructive sleep apnea (OSA) in adults during standard polysomnography sleep study conditions. The primary outcome metric is the Apnea-Hypopnea Index (AHI).

The goal, in its entirety, is to evaluate the performance of the Belun Ring Pulse Oximeter during a standard polysomnography sleep study and its ability to compare to the determined Apnea-Hypopnea Index (AHI) of the subjects. It is expected that the Belun Ring Pulse Oximeter will adequately record SpO₂, pulse rate, body position and heart rate variability throughout the duration of the study.

Background

Obstructive sleep apnea (OSA) is one of the most common disorders affecting sleep. Severe OSA is usually associated with significant morbidity and mortality of cardiovascular and pulmonary diseases. Polysomnography (PSG) is the current gold standard for diagnosing OSA. The Apnea-Hypopnea Index (AHI) derived from PSG monitoring is used to indicate the severity of OSA. The AHI values for adults are categorized as: AHI<5 = Normal, 5≤AHI<15 = Mild sleep apnea, 15≤AHI<30 = Moderate sleep apnea, and AHI≥30 = Severe sleep apnea.

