The study population will include a minimum of 50 competent adults, ages 18 to 90 years. The subject selection will be a mix of males and females including approximately 10 subjects with an AHI index <5, ten with an AHI index between 5 and 15, ten between 15 and 30 and ten >30.

The subjects must understand the study and consent to participate by signing the Informed Consent Form.

Subject enrollment is based on meeting the inclusion criteria and none of the exclusion criteria and the subject and data demographics needed for the study.

Inclusion Criteria

- Subject must have the ability to understand and provide written informed consent
- Subject is 18 to 90 years of age
- Subject must be willing and able to comply with study procedures and duration
- Male or female of any race

Exclusion Criteria

- Subject requires oxygen therapy or noninvasive ventilation
- Subject has a current diagnosis of chronic obstructive pulmonary disorder (COPD), neuromuscular disease, periodic limb movement, or narcolepsy.
- Compromised circulation, injury, or physical malformation of fingers, toes, hands, ears or forehead/skull or other sensor sites which would limit the ability to test sites needed for the study. (Note: Certain malformations may still allow subjects to participate if the condition is noted and would not affect the particular sites utilized.)
- Subject is on medication known to interfere with heart rate, such as beta blockers, digoxin, or calcium receptor agonists.
- Subjects with severe contact allergies to standard adhesives, latex or other materials found in pulse oximetry sensors, ECG electrodes, respiration monitor electrodes or other medical sensors (self-reported)
- Unwillingness or inability to remove colored nail polish from test digits.
- Other known health condition, which should be considered

Duration of Clinical Investigation

Each subject, and therefore use of the device, is expected to take 5-8 hours. The study is expected to take 2 - 4 months to complete for this subject population.

Participation in the study is voluntary. Subjects may choose to withdraw from the study at any point.

Procedure

1. Complete Equipment checkout list prior to starting study.
2. Set the clocks to sync data collection for the Belun ring pulse oximeter.

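### Pearson's r on raw AHI is labelled the ring's accuracy, but it mostly reflects the severe class and says little about ordering below AHI 30

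*Combined protocol and SAP*

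**What the plan says.** The Endpoint / Comparator section sets the primary objective as whether the ring gauges AHI correctly. It then assigns that task to one statistic: a Pearson's "correlation will be used to determine the accuracy performance of the sleep score generated by the Belun Ring Oximeter to the AHI score" from the PSG. The Statistical Analysis section is more neutral: "A Pearson's correlation between sleep score generated by the Belun software and AHI generated by the PSG analysis will be calculated". Neither section gives a transformation of AHI, a rank alternative, an analysis over part of the range, a confidence interval or a target value for r. The unit of the sleep score is not stated.

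Both sections also plan sensitivity and specificity at AHI 5, 15 and 30, and an area under the ROC curve. The cut-off for that area is not named, and no result carries an acceptance criterion.

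The Study Population section seeks "approximately 10 subjects with an AHI index <5, ten with an AHI index between 5 and 15, ten between 15 and 30 and ten >30". These groups add up to 40, while the minimum enrolment is 50. The Synopsis (Background) defines the top two classes as "15≤AHI<30 = Moderate sleep apnea, and AHI≥30 = Severe sleep apnea", so the severe class has no upper bound.

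**The concern.** Three of the four classes lie inside a 30-point range, and the fourth can extend well beyond it. A correlation computed on untransformed AHI weights subjects by their distance from the mean. Severe subjects therefore supply most of what it measures. Two of the three planned cut-offs, 5 and 15, lie in the part of the scale that contributes least.

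A score could thus fail to separate normal from mild, or mild from moderate, and still return a high r. Since r is the one statistic that the plan calls accuracy, a final report could quote a strong figure for a ring that performs poorly at two of its three screening cut-offs.

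**Working it through.** The plan states no target or expected r, so there is no figure to reproduce. The check asks what r would be for a ring with a known blind spot.

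**Inputs from the documents.** Class limits 0–5, 5–15, 15–30 and ≥30; about equal numbers per class.

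**Assumptions.** AHI is uniform within each class. The severe class runs from 30 to U, with U = 45, 60, 80 or 100.

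**Step 1: where the AHI variance lies.**
- Below 30, the class means are 2.5, 10 and 22.5, so the group mean is 11.67. The average within-class variance is (2.08 + 8.33 + 18.75)/3 = 9.72, and the variance of the class means is 68.06. The sub-30 variance is 77.78.
- The severe class has mean m = (30 + U)/2 and variance v = (U − 30)²/12.
- Total variance T = 0.75 × 77.78 + 0.25 v + 0.1875 (m − 11.67)².
- The share lying within the sub-30 group is S = 58.33/T.

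For U = 80: m = 55, v = 208.33, T = 58.33 + 52.08 + 352.08 = 462.5, and S = 0.13.

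**Step 2: a ring exact above 30 and uninformative below.** If its sub-30 scores are the AHI values shuffled at random, r = 1 − S. If it reports the sub-30 mean for everyone below 30, r = √(1 − S). For U = 80 these are 0.87 and 0.93. A bare severe/not-severe flag gives √(352.08/462.5) = 0.87.

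**Step 3: a ring with error above 30.** Below 30 the score is pure noise (mean 12, SD 7). Above 30 it is AHI plus error with SD e.
- Covariance with AHI: C = 0.1875 (m − 11.67)(m − 12) + 0.25 v.
- Score variance: V = 0.75 × 49 + 0.25 (v + e²) + 0.1875 (m − 12)².
- r = C/√(V T).

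For U = 80 and e = 10: C = 349.38 + 52.08 = 401.46; V = 36.75 + 77.08 + 346.69 = 460.52; r = 401.46/√(460.52 × 462.5) = 0.87.

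| Severe upper limit | S | r, shuffled below 30 | r, flag only | r, e = 10 | r, e = 15 |
|---|---|---|---|---|---|
| 45 | 0.31 | 0.69 | 0.82 | 0.68 | 0.63 |
| 60 | 0.20 | 0.80 | 0.85 | 0.79 | 0.75 |
| 80 | 0.13 | 0.87 | 0.87 | 0.87 | 0.84 |
| 100 | 0.08 | 0.92 | 0.88 | 0.91 | 0.89 |

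Simulation with ten per class agrees with the last two columns. With classes of 13/12/12/13 (n = 50), the lowest cell is 0.64 and the rest of those two columns change by at most about 0.01.

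**Step 4: what other measures show for the same ring** (simulation, e = 10, U = 60 to 100). Spearman's rho is 0.56–0.58. The correlation within AHI <30 averages 0.00. AUC is 0.66–0.67 at ≥5, 0.74–0.75 at ≥15 and about 0.99 at ≥30.

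**Step 5: precision of the sub-30 coefficient.** With 30 subjects and a true value of zero, the 95% range is ± tanh(1.96/√27) = ±0.36.

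**The case against.** The strongest reply is that the plan already contains the safeguard. The Objectives section gives the purpose as sensitivity and specificity, and both are planned at AHI 5 and 15, where the example ring fails. No decision is tied to r, and the accuracy wording appears only in Endpoint / Comparator. This largely stands, and it limits the point to labelling and reporting. One gap remains: a single ROC area is planned with no cut-off named. Reported at ≥30 it would be about 0.99 for this ring and would reinforce a misleading r.

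The second reply is that the example is extreme: blind below 30, yet almost perfect at 30. That is fair. The example shows what r can hide; it does not predict how this ring behaves. For a ring with ordinary uniform error (SD 7, severe limit 60), Pearson is 0.93 and Spearman 0.89, so the choice hardly matters.

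A reader might also infer that the class definitions make AHI strongly right-skewed. They do not. An open upper limit fixes no skew, and under the uniform assumptions skewness is only about 0.4 (limit 45) to 1.3 (limit 100).

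Finally, a reader might conclude that Spearman should replace Pearson. The objective of gauging AHI correctly does not support that: a score ten times AHI would have a rho of 1. Spearman is not a full cure either, since it rises to about 0.75 for such a ring if 20 of 50 subjects are severe.

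**Conclusion.** The point holds as a matter of labelling. Under the planned mix, only 8–31% of the AHI variance lies within the sub-30 range. A ring with no ordering there can give r anywhere from about 0.64 to 0.91, for severe limits of 45 to 100 and error SDs of 10 to 15. These figures rest on assumed distributions within classes, because the documents give none, and on a ring that still separates ≥30 from <30.

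Two stronger readings are not supported. The first is that r would be 0.8–0.9 whatever the sample: it falls to 0.63–0.69 for these rings if severe AHI stops at 45. The second is that the plan could not detect such a ring: sensitivity and specificity at 5 and 15 would show it. What needs correcting is that raw r, the measure least able to show this failure, is the one called accuracy.

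**What to change.** In Endpoint / Comparator and in Statistical Analysis:

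1. Describe Pearson's r as a measure of association, and state that raw r alone will not be cited as accuracy.
2. Beside it, report Spearman's rho over all subjects and the correlation within AHI <30, each with a 95% confidence interval.
3. Base the accuracy statement on sensitivity, specificity and a separate AUC at each of AHI 5, 15 and 30, with confidence intervals.
4. State the unit of the sleep score. If it is in AHI units, add Bland-Altman limits of agreement. For the example ring with error SD 10, the SD of the differences is about 11, so the limits would be about ±1.96 × 11 = ±22 events per hour, which would reveal the problem.

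The cost is a few sentences and a few lines of code, with no new data or subjects. The headline figure will probably be lower than raw r. The sub-30 coefficient will be imprecise, at roughly ±0.36 around zero with 30 subjects, so it should be read with its interval.
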